TITLE	Phase II Clinical and Pharmacokinetic Trial of PM00104 (Zalypsis®) in Patients with Advanced and/or Metastatic Endometrial or Cervical Cancer Previously Treated with One Line of Systemic Chemotherapy.
PROTOCOL CODE	PM104-B-001-09
INVESTIGATORS / TRIAL LOCATION	About 10 centers worldwide will participate in this trial. A full list of investigators will be available as a separate document.
STUDY OBJECTIVES Primary	
 • To evaluate the antitumor activity of PM00104 administered as a 1-hour intravenous (i.v.) infusion on Day 1, 8 and 15 every four weeks (d1, d8 and d15; q4wk) to patients with advanced and/or metastatic endometrial or cervical cancer previously treated with one line of systemic chemotherapy.
Secondary	
 • To determine the safety profile of this PM00104 regimen in these patients. • To determine the pharmacokinetic (PK) profile of this PM00104 regimen in these patients. • To determine the pharmacogenomic (PGx) profile of this PM00104 regimen in these patients. Hypothesis-generating exploratory PGx analyses will be conducted to correlate the molecular parameters found in the tumor and blood samples of the patients with the clinical results achieved with PM00104.
STUDY DESIGN	
Multicenter, open label, phase II clinical trial with single-agent PM00104 given as a 1-hour i.v. infusion on d1, d8 and d15 q4wk to patients with advanced and/or metastatic endometrial or cervical cancer in progression.
 
The primary endpoint of the study is the overall response rate (ORR), defined as the percentage of patients with objective response (OR; complete or partial response) as defined by the Response Evaluation Criteria in Solid Tumors (RECIST).
 
Treatment will be administered in the absence of disease progression and/or unacceptable toxicity. In case of obtaining a complete response, two additional cycles will be administered and then the treatment will be stopped.

STUDY POPULATION	
Adult female patients with endometrial or cervical cancer progressing after one previous line of systemic chemotherapy are eligible for this trial.
 
To be included in the study, patients have to fulfill all inclusion criteria and none of the exclusion criteria.

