
PHARMACOGENOMIC EVALUATIONS (only on samples collected in the U.S.)
	
Inclusion criteria for the PGx substudy:
 
 • All patients included in trial PM104-B-001-09 will be eligible. • Only those patients with available tissue samples that voluntarily sign the Informed Consent Form for the PGx substudy will participate. 
Exclusion criteria for the PGx substudy:
 
 • Patients who do not consent to participate in this substudy. Refusal to participate in the PGx substudy will not affect participation in the main trial PM104-B-001-09. 
The aim of this investigation is to identify and validate molecular markers whose expression may be associated with the clinical outcome of patients treated with PM00104. These molecular markers might allow the identification of those patients who will benefit from the treatment with PM00104, thus improving the health care by an individualized medicine.
 
The following analyses will be done on tumor and blood samples from consenting patients treated with PM00104:
 
 ♦ Quantitation of mRNA expression in paraffin-embedded tumor tissue by real-time quantitative reverse transcriptase polymerase chain reaction (PCR) of genes identified during in vitro studies as potential biomarkers of response to PM00104. These genes will be selected from BRCA1, ERCC1, XPG, RAD51, TOP2A and TOP1 and other genes related to the mechanism of action of PM00104. ♦ Quantitation of protein expression by immunohistochemistry in tissue microarrays constructed from the patient's paraffin-embedded tumor tissue blocks. The proteins to be determined include XPG, ERCC1, XPA, BRCA1, RAD51, BRCA2, ATM, CDK7, CHK1, MDM2, DNAPola, CHK2, DNA-PK, p16, p21, p53, and other proteins related to the mechanism of action of PM00104. ♦ Analysis of single nucleotide polymorphisms (SNP) at the gene XPG will be done, including those at positions 1104, 1080 and 1053 and SNPs of other genes related to the mechanism of action of PM00104.

STATISTICAL METHODS
	
Primary Endpoint:
 
 • Overall response rate (ORR), defined as the percentage of patients with confirmed objective response (OR), either complete (CR) or partial (PR) response according to the RECIST.

Secondary Endpoints:

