8.4. PHARMACOGENOMIC SUBSTUDY (ONLY ON SAMPLES COLLECTED IN THE U.S.)

The pharmacogenomic (PGx) profile of PM00104 is a secondary endpoint of this study to be evaluated in a PGx substudy. The aim of this PGx substudy is to identify and validate molecular markers whose expression may be associated with the clinical outcome of patients treated with PM00104. These molecular markers might allow the identification of those patients who will benefit from the treatment with PM00104, improving the health care by an individualized medicine.

The objectives of this PGx substudy are:

1. To determine the gene and protein expression profiles of selected genes in tumor tissue of the patients included in the clinical study PM104-B-001-09.
2. To determine the genotype of the SNP Asp1104His of XPG and other SNPs related to the mechanism of action of PM00104.
3. To correlate the gene and protein expression profiles and the SNP genotype with the clinical outcome of the patients and the evolution of the disease.
4. To validate in patient tumor samples selected putative markers of sensitivity to PM00104 found during *in vitro* studies

[Appendix 1. Samples, Methodology and Techniques of the Pharmacogenomic Substudy](#) includes a detailed protocol for sample collection and analysis. Briefly, the samples required for the molecular characterization analyses will be blood samples taken prior to the first PM00104 infusion and paraffin-embedded tumor tissue slices obtained at disease diagnosis from patients included in the trial who accepted to participate in the PGx substudy.

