- h. Statistics: clinical data and immunohistochemistry scoring are performed blind, and data are compiled only after all analyses are completed. Fisher's exact test is used to test whether a specific protein-expression profile is associated with the clinical outcome after Zalypsis[®] treatment. Significance is concluded for values of $p < 0.05$. The prognosis value of markers will be explored for objective clinical response, progression free survival and survival. In each case, a multivariate model is developed by backwards elimination, starting with all markers with a p-value lower than 0.10 in the univariate analysis. Hazard ratios will be calculated with the univariate Cox model, and comparison between Kaplan-Meier survival and progression free survival curves will be performed with the log-rank test. All tests of statistical significance are two-sided, and significance is set at 0.05 except in multiple comparisons, where it is set at 0.017 in accordance with the Bonferroni correction.

References:

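### Pharmacogenomic models built by a p<0.10 screen and backwards elimination on the same patients will overstate marker effects, and the response model will often be empty or separated when responders are few

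*Protocol*

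**What the plan says.** Protocol Appendix 1, section 4, item h sets three outcomes: "The prognosis value of markers will be explored for objective clinical response, progression free survival and survival". For each, "a multivariate model is developed by backwards elimination, starting with all markers with a p-value lower than 0.10 in the univariate analysis". It gives no p-value for staying in the model, no minimum number of events, no shrinkage, no resampling and no rule for a separated marker. It names Fisher's exact test for protein profiles, takes hazard ratios from univariate Cox models, and sets significance at 0.05, or 0.017 for multiple comparisons.

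The candidates are in the synopsis, under pharmacogenomic evaluations:
- mRNA: "These genes will be selected from BRCA1, ERCC1, XPG, RAD51, TOP2A and TOP1" (6)
- proteins: "XPG, ERCC1, XPA, BRCA1, RAD51, BRCA2, ATM, CDK7, CHK1, MDM2, DNAPola, CHK2, DNA-PK, p16, p21, p53" (16)
- XPG polymorphisms: "including those at positions 1104, 1080 and 1053" (3)

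Each list is left open to further markers. The work is done "only on samples collected in the U.S", with optional consent and available tissue, while "About 10 centers worldwide will participate in this trial". The U.S. share is not given.

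Protocol sections 2.2 and 10.3.4 call these analyses hypothesis-generating. Section 8.4 nevertheless lists as an objective "To validate in patient tumor samples selected putative markers of sensitivity to PM00104". SAP section 8 leaves the pharmacogenomic analysis to a separate document, so item 4h is the only specification available here.

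**The concern.** A marker enters the model only if its estimate in these patients is already large, and it stays only if the estimate remains large beside the others. Nothing afterwards allows for that selection. The surviving hazard ratios are therefore too far from 1, and the model's apparent discrimination is too good. A stricter significance level changes how many markers survive; it does not shrink the survivors.

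The response model has a further difficulty. When responders are few, the tables extreme enough to pass a p<0.10 screen may be those with every responder on one side of the marker. Ordinary logistic regression then has no finite odds ratio.

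At stake is a secondary objective. The substudy is meant to find markers that could identify patients who benefit, and the effect sizes carried forward would mislead the design of any later study.

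**Working it through.** **Inputs from the documents.** Named markers: 6 + 16 + 3 = 25. Planned evaluable patients: 30 + 32 = 62 (Protocol section 10.1). Second-line median PFS of 2 months and OS of 6-8 months (section 1.4), so nearly every patient has an event. Response rates of 5% to 30% span the null and alternative hypotheses. **Assumed:** a U.S. subset of about 15 to 40, with 62 as the ceiling; roughly even marker splits; tumour groups pooled.

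**The plan's own figure.** 0.05/3 = 0.0167, which rounds to the stated 0.017. It covers three comparisons, is not tied to the 0.10 screen, and is not stated to be a stay level.

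**Chance entry.** With 25 independent null markers, 25 × 0.10 = 2.5 are expected to pass, and the chance that at least one passes is 1 − 0.90^25 = 93%.

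**Smallest hazard ratio that can pass.** For an evenly split marker and d events, the log hazard ratio has standard error of about 2/√d. Passing needs a ratio of at least exp(1.645 × 2/√d), or its inverse. That is 2.09 at d = 20, 1.82 at d = 30 and 1.52 at d = 62. Any such marker that passes therefore shows at least this much effect, even when the truth is 1.0.

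**Simulated Cox models, no true effects** (univariate screen at 0.10, then backwards elimination; several independent runs of 150-400 datasets per setting). Ratios are expressed as greater than 1.

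| Patients | Median retained hazard ratio | Median univariate ratio of screened-in markers |
|---|---|---|
| 20 | about 4.5-6 | 2.9-3.0 |
| 30 | about 3-4 | 2.3 |
| 62 | about 2 | 1.7 |

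- Stay level 0.05: at least one marker is retained in about 75-85% of datasets (80% at n = 62).
- Stay level 0.017: at least one is retained in about 35-50%. One set of 150 runs each gave 36% at n = 20, 49% at 30, 45% at 40 and 35% at 62, each with a standard error of about √(0.4 × 0.6/150) = 4 points.
- Markers correlated at 0.3-0.5, stay level 0.05, n = 20 and 30: 64-78% retain at least one, with median ratios of 4.0-4.2 and 2.8-3.0.
- Apparent C-index, stay level 0.05: 0.69, 0.67 and 0.64 at n = 20, 30 and 40, where the truth is 0.50.

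**Response, exact Fisher tables, evenly split marker.** With r responders among n patients, the fully separated table has two-sided p = 2·C(n/2, r)/C(n, r). For n = 24 and r = 4 this is 2 × 495/10,626 = 0.093.

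| Responders | p, separated table (n = 16-30) | p, next table |
|---|---|---|
| 3 | 0.20-0.22 | larger |
| 4 | 0.077-0.100 | 0.57-0.60 |
| 6 | 0.007-0.017 | 0.12-0.17 |

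With 3 responders nothing passes. With 4 or 6, only a separated marker passes. At least one of 25 null markers does so in 86-93% of datasets with 4 responders (for n = 16, 1 − (1 − 0.0769)^25 = 86%), but in only 16-35% with 6, so the model is empty in 65-84%. With 7 responders a non-separated table can pass: at n = 24, p = (2 × 792 + 2 × 12 × 924)/346,104 = 0.069.

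**Response, simulated with mixed marker types, n = 15-30, response rate 5-30%:**
- Fisher screen (rank test for continuous markers): separated or no responders in 16-60%; no marker enters in 17-52%.
- Likelihood-ratio screen: separated or no responders in 54-94%, except 23% at n = 30 with a 30% response rate.
- Wald screen: separated in 0-14%; at response rates of 5-10% no marker enters in 58-76%.

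At n = 62 with a 20% response rate, separation falls to about 5%.

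**The case against.** Four points on the other side deserve weight.

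- **Status.** The analyses are labelled hypothesis-generating, they do not enter the two-stage or toxicity rules, and a separate document may already handle this. That lowers the priority. It does not correct the estimates, and the stated objective of validation pulls the other way.
- **Univariate hazard ratios.** Item 4h reports univariate ratios, which are less inflated than the multivariable ones (2.9-3.0 against about 4.5-6 at n = 20). This stands. For selected markers they are still well above 1.
- **Stay level.** A reader might infer that most signal-free datasets would yield a marker model. That holds at a stay level of 0.05 but not at 0.017, and the plan gives neither.
- **Response model.** A reader might infer that the response model usually has no finite estimate. The documents do not support this. Separation in about 90% of datasets needs four responders and evenly split markers. With 4 responders and a 40/60 split, at n = 20-30, no marker passes in 61-70% of datasets. mRNA levels are quantitative and need not form a 2×2 table, and item 4h does not fix the screening test for response.

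Nor do the documents establish that the subset is very small. They give no U.S. number, and at 62 patients the inflation is about twofold.

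**Conclusion.** The concern holds in a limited form. At every subset size examined, up to the 62 planned evaluable patients, the rule as written gives selected hazard ratios biased away from 1: about 4.5-6 at 20 patients, 3-4 at 30 and 2 at 62, with smaller inflation in the univariate ratios. The 0.017 level does not remove this. How often a chance marker survives depends on the unstated stay level. How often the response model is empty or separated depends on the number of responders, the marker splits and the screening test.

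The sizes rest on an assumed subset size, marker prevalence and pooling of the tumour groups. If the groups were modelled separately, the ceilings would be 30 and 32 evaluable patients. Correlation between markers lowers the retention figures somewhat. This is a lower-priority point: it bears on a secondary objective, and the primary analysis is untouched.

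**What to change.** Amend Appendix 1, item 4h, or put the following in the separate pharmacogenomic analysis document:

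1. Report univariate estimates with confidence intervals for every marker tested, not only those selected.
2. For any multivariable Cox model, repeat the whole screening and elimination procedure in bootstrap samples and report optimism-corrected estimates and C-index; or use a penalised Cox model instead. If selection is kept, state the screening test and the stay level.
3. Do not report an ordinary maximum-likelihood multivariable response model when responders are few or a marker is separated. Use Firth-type estimation, or give univariate results only.
4. In the synopsis, section 8.4 and Appendix 1, describe the output as marker identification rather than validation.

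Penalised models are themselves unstable with 25 or more markers in about 20 patients, so items 1 and 4 matter whichever model is chosen. The cost is a paragraph of text, a little more programming, and estimates that are shrunken and look less favourable. No patient procedure changes.

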Appendix 2. ECOG Performance Status Assessment Scale

Grade	Activity
0	Able to carry on all normal activities without restriction.
1	Restricted in physically strenuous activity but ambulatory and able to carry out light work.
2	Ambulatory and capable of all self-care but unable to carry out any work activities. Up and about more than 50% of waking hours.
3	Capable of only limited self-care, confined to bed or chair more than 50% of waking hours.
4	Completely disabled. Cannot carry on any self-care. Totally confined to bed or chair.

Appendix 3. Cockcroft and Gault Formula

$$\text{Creatinine clearance (ml/min)} = \frac{[(140 - \text{age (years)}) \times \text{weight (Kg)}]}{72 \times \text{serum creatinine (mg/dl)}} \times G^1$$

¹G (Gender) = 0.85 if female; 1 if male.

Reference: Cockcroft, DW, Gault, H. Prediction of creatinine clearance from serum creatinine. *Nephron* 1976;16(1):31-41.

Appendix 4. Evaluation of Response. The RECIST

Measurability of tumor lesions at baseline

Definitions

Measurable disease - the presence of at least one measurable lesion. If the measurable disease is restricted to a solitary lesion, its neoplastic nature should be pathologically confirmed.

Measurable lesions - lesions that can be accurately measured in at least one dimension with longest diameter ≥ 20 mm. With spiral CT scan, lesions must be ≥ 10 mm in at least one dimension.

Non-measurable lesions - all other lesions, including small lesions (longest diameter < 20 mm with conventional techniques or < 10 mm with spiral CT scan) and other non-measurable lesions. These include: bone lesions, leptomeningeal disease, ascites, pleural/pericardial effusion, inflammatory breast disease, cutaneous or pulmonary lymphangitis, abdominal masses that are not confirmed and followed by imaging techniques, and cystic lesions.

All measurements should be recorded in metric notation using a ruler or calipers. All baseline evaluations should be performed as closely as possible to the beginning of treatment and never more than four weeks before the beginning of the treatment.

For the present study, lesions in irradiated area are considered as measurable provided radiotherapy has ended three months prior to entry, and they have progressed or appeared since then. They must satisfy the previous criteria.

Methods of measurements

The same method of assessment and the same technique should be used to characterize each identified and reported lesion at baseline and during follow-up.

Clinically detected lesions will only be considered measurable when they are superficial (e.g. skin nodules, palpable lymph nodes). For the case of skin lesions, documentation by color photography -including a ruler to estimate the size of the lesion- is recommended.

Lesions on chest X-ray are acceptable as measurable lesions when they are clearly defined and surrounded by aerated lung. However, CT is preferable.

CT and MRI are the best currently available and reproducible methods to measure target lesions selected for response assessment. Conventional CT and MRI should be performed with contiguous cuts of 10 mm or less in slice thickness. Spiral CT should be performed using a 5-mm contiguous reconstruction algorithm; this specification applies to the tumors of the chest, abdomen and pelvis, while head and neck tumors and those of the extremities usually require specific protocols.

Ultrasound (US) should not be used to measure tumor lesions that are clinically not easily accessible. It may be used as a possible alternative to clinical measurements of superficial palpable nodes, subcutaneous lesions and thyroid nodules. US might also be useful to confirm the complete disappearance of superficial lesions usually assessed by clinical examination.

Tumor response evaluation

Baseline documentation of “Target” and “Non-Target” lesions

All measurable lesions up to a maximum of five lesions per organ and 10 lesions in total, representative of all involved organs, should be identified as target lesions and will be recorded and measured at baseline.

Target lesions should be selected on the basis of their size (those with the longest diameter) and their suitability for accurate repetitive measurements (either by imaging techniques or clinically).

A sum of the longest diameter (LD) for all target lesions will be calculated and reported as the baseline sum LD. The baseline sum LD will be used as reference by which to characterize the objective tumor response.

All other lesions (or sites of disease) should be identified as non-target lesions and should also be recorded at baseline. Measurements are not required but the presence or absence of each should be noted throughout follow-up.

Response Criteria

Evaluation of target lesions

- * **Complete Response (CR):** Disappearance of all target lesions.
- * **Partial Response (PR):** At least a 30% decrease in the sum of LD of target lesions, taking as reference the baseline sum LD.
- * **Progression (PD):** At least a 20% increase in the sum of LD of target lesions, taking as references the smallest sum LD recorded since the treatment started or the appearance of one or more new lesions.
- * **Stable Disease (SD):** Neither sufficient shrinkage to qualify for PR nor sufficient increase to qualify for PD, taking as references the smallest sum LD since the treatment started.

Evaluation of non target lesions

- * **Complete Response (CR):** Disappearance of all non-target lesions and normalization of tumor marker level.
- * **Incomplete Response / Stable Disease** / Persistence of one or more non-target lesion(s) and/or maintenance of tumor marker level above the normal limits.
- * **Progression (PD):** Appearance of one or more new lesions and/or unequivocal progression of existing non-target lesions.

Evaluation of best overall morphological response

The best overall morphological response is the best response recorded from the start of the treatment until disease progression/recurrence (taking as reference for progressive disease the smallest measurements recorded since the treatment started).

To be assigned a status of PR or CR, changes in tumor measurements must be confirmed by repeat assessments that should be performed not less than four weeks after the criteria for response were first met. If PR or CR is found at Week 6, it is recommended that response is confirmed using the evaluation scheduled at Week 12.

In the case of SD, follow-up measurements must have met the SD criteria at least once after study entry, at a minimum 6-week interval.

Target lesions	Non-target lesions	New lesions	Overall response
CR	CR	No	CR
CR	Incomplete response / SD	No	PR
PR	Non-PD	No	PR
SD	Non-PD	No	SD
PD	Any	Yes or No	PD
Any	PD	Yes or No	PD
Any	Any	Yes	PD

CR, complete response; PD, progressive disease; PR, partial response; SD, stable disease.

Every effort should be made to document objective progression, even after discontinuation of treatment.

Appendix 5. Declaration of Helsinki

WORLD MEDICAL ASSOCIATION DECLARATION OF HELSINKI **Ethical Principles for Medical Research Involving Human Subjects**

Adopted by the 18th WMA General Assembly, Helsinki, Finland, June 1964, and amended by the:

29th WMA General Assembly, Tokyo, Japan, October 1975

35th WMA General Assembly, Venice, Italy, October 1983

41st WMA General Assembly, Hong Kong, September 1989

48th WMA General Assembly, Somerset West, Republic of South Africa, October 1996

52nd WMA General Assembly, Edinburgh, Scotland, October 2000

53th WMA General Assembly, Washington 2002 (Note of Clarification on paragraph 29 added)

55th WMA General Assembly, Tokyo 2004 (Note of Clarification on paragraph 30 added)

59th WMA General Assembly, Seoul, October 2008

A. INTRODUCTION

1. The World Medical Association (WMA) has developed the Declaration of Helsinki as a statement of ethical principles for medical research involving human subjects, including research on identifiable human material and data.
The Declaration is intended to be read as a whole and each of its constituent paragraphs should not be applied without consideration of all other relevant paragraphs.
2. Although the Declaration is addressed primarily to physicians, the WMA encourages other participants in medical research involving human subjects to adopt these principles.
3. It is the duty of the physician to promote and safeguard the health of patients, including those who are involved in medical research. The physician's knowledge and conscience are dedicated to the fulfilment of this duty.
4. The Declaration of Geneva of the WMA binds the physician with the words, "The health of my patient will be my first consideration," and the International Code of Medical Ethics declares that, "A physician shall act in the patient's best interest when providing medical care."
5. Medical progress is based on research that ultimately must include studies involving human subjects. Populations that are underrepresented in medical research should be provided appropriate access to participation in research.
6. In medical research involving human subjects, the well-being of the individual research subject must take precedence over all other interests.

7. The primary purpose of medical research involving human subjects is to understand the causes, development and effects of diseases and improve preventive, diagnostic and therapeutic interventions (methods, procedures and treatments). Even the best current interventions must be evaluated continually through research for their safety, effectiveness, efficiency, accessibility and quality.
8. In medical practice and in medical research, most interventions involve risks and burdens.
9. Medical research is subject to ethical standards that promote respect for all human subjects and protect their health and rights. Some research populations are particularly vulnerable and need special protection. These include those who cannot give or refuse consent for themselves and those who may be vulnerable to coercion or undue influence.
10. Physicians should consider the ethical, legal and regulatory norms and standards for research involving human subjects in their own countries as well as applicable international norms and standards. No national or international ethical, legal or regulatory requirement should reduce or eliminate any of the protections for research subjects set forth in this Declaration.

B. BASIC PRINCIPLES FOR ALL MEDICAL RESEARCH

11. It is the duty of physicians who participate in medical research to protect the life, health, dignity, integrity, right to self-determination, privacy, and confidentiality of personal information of research subjects.
12. Medical research involving human subjects must conform to generally accepted scientific principles, be based on a thorough knowledge of the scientific literature, other relevant sources of information, and adequate laboratory and, as appropriate, animal experimentation. The welfare of animals used for research must be respected.
13. Appropriate caution must be exercised in the conduct of medical research that may harm the environment.
14. The design and performance of each research study involving human subjects must be clearly described in a research protocol. The protocol should contain a statement of the ethical considerations involved and should indicate how the principles in this Declaration have been addressed. The protocol should include information regarding funding, sponsors, institutional affiliations, other potential conflicts of interest, incentives for subjects and provisions for treating and/or compensating subjects who are harmed as a consequence of participation in the research study. The protocol should describe arrangements for post-study access by study subjects to interventions identified as beneficial in the study or access to other appropriate care or benefits.
15. The research protocol must be submitted for consideration, comment, guidance and approval to a research ethics committee before the study begins. This committee must be independent of the researcher, the sponsor and any other undue influence. It must take into consideration the laws and regulations

of the country or countries in which the research is to be performed as well as applicable international norms and standards but these must not be allowed to reduce or eliminate any of the protections for research subjects set forth in this Declaration. The committee must have the right to monitor ongoing studies. The researcher must provide monitoring information to the committee, especially information about any serious adverse events. No change to the protocol may be made without consideration and approval by the committee.

16. Medical research involving human subjects must be conducted only by individuals with the appropriate scientific training and qualifications. Research on patients or healthy volunteers requires the supervision of a competent and appropriately qualified physician or other health care professional. The responsibility for the protection of research subjects must always rest with the physician or other health care professional and never the research subjects, even though they have given consent.
17. Medical research involving a disadvantaged or vulnerable population or community is only justified if the research is responsive to the health needs and priorities of this population or community and if there is a reasonable likelihood that this population or community stands to benefit from the results of the research.
18. Every medical research study involving human subjects must be preceded by careful assessment of predictable risks and burdens to the individuals and communities involved in the research in comparison with foreseeable benefits to them and to other individuals or communities affected by the condition under investigation.
19. Every clinical trial must be registered in a publicly accessible database before recruitment of the first subject.
20. Physicians may not participate in a research study involving human subjects unless they are confident that the risks involved have been adequately assessed and can be satisfactorily managed. Physicians must immediately stop a study when the risks are found to outweigh the potential benefits or when there is conclusive proof of positive and beneficial results.
21. Medical research involving human subjects may only be conducted if the importance of the objective outweighs the inherent risks and burdens to the research subjects.
22. Participation by competent individuals as subjects in medical research must be voluntary. Although it may be appropriate to consult family members or community leaders, no competent individual may be enrolled in a research study unless he or she freely agrees.
23. Every precaution must be taken to protect the privacy of research subjects and the confidentiality of their personal information and to minimize the impact of the study on their physical, mental and social integrity.
24. In medical research involving competent human subjects, each potential subject must be adequately informed of the aims, methods, sources of funding, any possible conflicts of interest, institutional affiliations of the

researcher, the anticipated benefits and potential risks of the study and the discomfort it may entail, and any other relevant aspects of the study. The potential subject must be informed of the right to refuse to participate in the study or to withdraw consent to participate at any time without reprisal. Special attention should be given to the specific information needs of individual potential subjects as well as to the methods used to deliver the information. After ensuring that the potential subject has understood the information, the physician or another appropriately qualified individual must then seek the potential subject's freely-given informed consent, preferably in writing. If the consent cannot be expressed in writing, the non-written consent must be formally documented and witnessed.

25. For medical research using identifiable human material or data, physicians must normally seek consent for the collection, analysis, storage and/or reuse. There may be situations where consent would be impossible or impractical to obtain for such research or would pose a threat to the validity of the research. In such situations the research may be done only after consideration and approval of a research ethics committee.
26. When seeking informed consent for participation in a research study the physician should be particularly cautious if the potential subject is in a dependent relationship with the physician or may consent under duress. In such situations the informed consent should be sought by an appropriately qualified individual who is completely independent of this relationship.
27. For a potential research subject who is incompetent, the physician must seek informed consent from the legally authorized representative. These individuals must not be included in a research study that has no likelihood of benefit for them unless it is intended to promote the health of the population represented by the potential subject, the research cannot instead be performed with competent persons, and the research entails only minimal risk and minimal burden.
28. When a potential research subject who is deemed incompetent is able to give assent to decisions about participation in research, the physician must seek that assent in addition to the consent of the legally authorized representative. The potential subject's dissent should be respected.
29. Research involving subjects who are physically or mentally incapable of giving consent, for example, unconscious patients, may be done only if the physical or mental condition that prevents giving informed consent is a necessary characteristic of the research population. In such circumstances the physician should seek informed consent from the legally authorized representative. If no such representative is available and if the research cannot be delayed, the study may proceed without informed consent provided that the specific reasons for involving subjects with a condition that renders them unable to give informed consent have been stated in the research protocol and the study has been approved by a research ethics committee. Consent to remain in the research should be obtained as soon as possible from the subject or a legally authorized representative.

30. Authors, editors and publishers all have ethical obligations with regard to the publication of the results of research. Authors have a duty to make publicly available the results of their research on human subjects and are accountable for the completeness and accuracy of their reports. They should adhere to accepted guidelines for ethical reporting. Negative and inconclusive as well as positive results should be published or otherwise made publicly available. Sources of funding, institutional affiliations and conflicts of interest should be declared in the publication. Reports of research not in accordance with the principles of this Declaration should not be accepted for publication.

C. ADDITIONAL PRINCIPLES FOR MEDICAL RESEARCH COMBINED WITH MEDICAL CARE

31. The physician may combine medical research with medical care only to the extent that the research is justified by its potential preventive, diagnostic or therapeutic value and if the physician has good reason to believe that participation in the research study will not adversely affect the health of the patients who serve as research subjects.
32. The benefits, risks, burdens and effectiveness of a new intervention must be tested against those of the best current proven intervention, except in the following circumstances:
 - a. The use of placebo, or no treatment, is acceptable in studies where no current proven intervention exists; or
 - b. Where for compelling and scientifically sound methodological reasons the use of placebo is necessary to determine the efficacy or safety of an intervention and the patients who receive placebo or no treatment will not be subject to any risk of serious or irreversible harm. Extreme care must be taken to avoid abuse of this option.
33. At the conclusion of the study, patients entered into the study are entitled to be informed about the outcome of the study and to share any benefits that result from it, for example, access to interventions identified as beneficial in the study or to other appropriate care or benefits.
34. The physician must fully inform the patient which aspects of the care are related to the research. The refusal of a patient to participate in a study or the patient's decision to withdraw from the study must never interfere with the patient-physician relationship.
35. In the treatment of a patient, where proven interventions do not exist or have been ineffective, the physician, after seeking expert advice, with informed consent from the patient or a legally authorized representative, may use an unproven intervention if in the physician's judgement it offers hope of saving life, re-establishing health or alleviating suffering. Where possible, this intervention should be made the object of research, designed to evaluate its safety and efficacy. In all cases, new information should be recorded and, where appropriate, made publicly available.
